**Table 7. Rules for Determining Carriage Status**

No. Positive Results							
No. Visits Available	0	1	2	3	4	5	6
1	Missing	Missing	N/A	N/A	N/A	N/A	N/A
2	Missing	Intermittent	Intermittent	N/A	N/A	N/A	N/A
3	Indeterminate	Indeterminate	Indeterminate	Indeterminate	N/A	N/A	N/A
4	Indeterminate	Indeterminate	Indeterminate	Indeterminate	Indeterminate	N/A	N/A
5	Noncarrier	Intermittent	Intermittent	Intermittent	Persistent	Persistent	N/A
6	Noncarrier	Intermittent	Intermittent	Intermittent	Intermittent	Persistent	Persistent

Abbreviation: N/A = not applicable.

3. Acquisition is defined as a positive swab at any postsurgery visit, given that the results for the vaccination and presurgery visits were both negative. The proportions of acquisitions will be compiled for each subsequent postsurgery visit and “any postsurgery visit.” The denominator at each visit will be the number of subjects with at least 1 nonmissing swab result. Acquisition will be compiled for nose, throat, and “any anatomical site.”
4. Clearance is defined as 2 consecutive postbaseline negative swabs, given that all preceding swabs were positive. The proportions of clearances will be compiled for each postbaseline visit. The denominator at each visit will be the number of subjects with at least 1 nonmissing swab result. The analyses will be performed for nose, throat, and “any anatomical site.”

Colonization, carriage status, acquisition, and clearance will be compiled for “any *S aureus*,” MRSA, and methicillin-sensitive *S aureus* (MSSA).

Capsule type will be identified for each *S aureus* isolate as either CP5 or CP8. A small subset of isolates will be neither capsule type, so these isolates will be considered missing for capsule type. Carriage status, acquisition, and clearance will be obtained for each capsule type. These endpoints will be identified as capsule-type persistence, capsule-type intermittent, capsule-type noncarrier, capsule-type acquisition, and capsule-type clearance. Analyses with these endpoints may be performed.

Other endpoints based on clonal complex (CC) and sequence type (ST) may be explored. *S aureus* protein A (*Spa*) typing and capsule typing may be examined only for PDIs with microbiologically confirmed *S aureus* infection.

Colonization results obtained after a culture-confirmed efficacy endpoint will not be included in deriving characterizations or acquisition. Results from unscheduled visits will not be included in characterizations for persistence, intermittent, etc.

Statistical methodology for colonization is described in [Section 8.1.3.4](#).

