1. INTRODUCTION

Staphylococcus aureus (*S aureus*) is a gram-positive coccus and a commensal organism that colonizes the nares, axillae, pharynx, and other mucosal and skin surfaces of approximately 20% to 50% of humans.^{1,2} *S aureus* is an opportunistic pathogen² and a leading cause of healthcare-associated infections (HAIs), including bloodstream infection (BSI), surgical-site infection (SSI), and hospital-acquired pneumonia (HAP),^{2,3} and is an increasingly common cause of community-associated infections in the United States (US), Europe, and globally. Among North American, Latin American, European, and Western Pacific nations, *S aureus* is recognized as the leading cause of HAIs.⁴ In the United States, *S aureus* is estimated to represent 15% of all HAIs.⁵ In the outpatient setting, *S aureus* has been estimated to be responsible for 11.6 million skin and soft tissue infections (SSTIs) annually in the United States, affecting 411/10,000 persons.⁶ Likewise, globally *S aureus* is the predominant cause of SSTI, representing 45% of North American, 34% of Latin American, and 38% of European isolates.⁷

The widespread disease manifestations of *S aureus* and its substantial burden to the healthcare system present a serious unmet medical need. Infections due to methicillin-sensitive *S aureus* (MSSA) as well as those due to methicillin-resistant *S aureus* (MRSA) contribute to disease morbidity, mortality, and economic burden, as well as the increasing need for more rigorous infection control practices. Despite the availability of antibiotics indicated for the prevention and treatment of *S aureus* infections, outcomes remain suboptimal for many patients.² Given the failure of the current standards of care to address the global epidemic of *S aureus* disease, the need for a preventive vaccine is clear.

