#### **5.4.2. mITT Colonization Population**

The mITT colonization population includes all randomized subjects who had at least 1 valid colonization swab sample result.

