#### **8.1.3.4. Colonization with *Staphylococcus aureus***

Colonization values obtained up to 7 days before vaccination until the day of admission for surgery will be considered eligible baseline values.

Colonization at each visit, acquisition, and clearance are binary endpoints, so they will be summarized with proportions. Vaccine groups will be compared using the CMH test. Site will be the stratification variable.

Carriage status will form a  $3 \times 2$  table with 3 categories—“persistent,” “intermittent,” and “noncarrier”—and 2 vaccine groups. “Indeterminate” will be considered a missing value. Vaccine groups will be compared using the CMH test. Site will be the stratification variable.

Subgroup analyses will be performed by executing logistic regressions with the dependent variable of the proportion of subjects colonized. The model terms will be vaccine group, subgroup, and vaccine group–subgroup interaction. The colonization results for subgroups with significant interactions, defined as  $p < 0.10$ , will be examined more closely.

One subgroup will be examined at a time. Anatomical sites will be examined separately. Only colonization at scheduled visits will be included. Only *S aureus* colonization will be analyzed because the purpose is to see if vaccine group has different effects within subgroup levels.

Vaccine groups will be compared using the Fisher exact test, 2-sided, for the proportion positive for *S aureus* from unscheduled visits. Stratification by clinical site is not proposed because the unscheduled visits will presumably be associated with possible BSI/SSI/ISA.

The number of these assessments per site should be low. Analyses will be performed by anatomical site and for anatomical sites combined.

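### SAP 6.3.4 defines acquisition and clearance for subjects at risk but divides by everyone with a swab, so the printed proportions understate both, clearance most

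*SAP*

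**What the plan says.** SAP Section 6.3.4, endpoints 3 and 4 (printed after Table 7), gives the two definitions:

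- Endpoint 3: "Acquisition is defined as a positive swab at any postsurgery visit, given that the results for the vaccination and presurgery visits were both negative".
- Endpoint 4: "Clearance is defined as 2 consecutive postbaseline negative swabs, given that all preceding swabs were positive".

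The same denominator sentence follows each: "The denominator at each visit will be the number of subjects with at least 1 nonmissing swab result".

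The analysis set does not narrow this. SAP Section 5.4.2: "The mITT colonization population includes all randomized subjects who had at least 1 valid colonization swab sample result". On method, SAP Section 8.1.3.4 says: "Colonization at each visit, acquisition, and clearance are binary endpoints, so they will be summarized with proportions". The arms are then compared by a CMH test stratified by site. Table 25 states the aim as exploring what vaccination does to acquiring and to clearing the organism, repeated for any S aureus, MRSA and MSSA, and adds no restriction. Protocol Section 9.3.4.2 defines neither endpoint.

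**The concern.** Each definition carries a condition that its denominator ignores. A subject colonized before surgery cannot acquire in the SAP's sense, yet is counted as not having acquired. A subject who was never positive cannot clear, yet is counted as not having cleared. Followed literally, the table rows would be read as the risk of acquiring or of clearing S aureus but would be something smaller.

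The printed proportion also moves with the share of subjects at risk. The presurgery swab is taken 10 to 60 days after vaccination under the protocol's schedule, so that share could differ between arms. Lower carriage on SA4Ag before surgery would then show up as more acquisition and less clearance on SA4Ag, even if the at-risk rates were identical.

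**Working it through.** The documents give no acquisition rate, clearance rate or power for these endpoints, so there is no planned figure to reproduce. All rates below are assumptions.

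**Inputs.** Let a be the acquisition proportion among subjects at risk, and c the share of swabbed subjects who are ineligible because they were positive at vaccination or before surgery. Let k be the clearance proportion among subjects at risk, and e the share of swabbed subjects whose earlier swabs were all positive. The assumed range for c and e is 20% to 50%. It is borrowed from the Protocol Introduction, which says that S aureus "colonizes the nares, axillae, pharynx, and other mucosal and skin surfaces of approximately 20% to 50% of humans". That is a background figure over several body sites, whereas this trial swabs nose and throat only.

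**Formulas.** Printed acquisition = a × (1 − c). Printed clearance = k × e.

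**Dilution, with a = 10% and k = 40% assumed.**

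| Assumed share (c or e) | Printed acquisition | Printed clearance |
|---|---|---|
| 20% | 0.10 × 0.80 = 8.0% | 0.40 × 0.20 = 8.0% |
| 35% | 0.10 × 0.65 = 6.5% | 0.40 × 0.35 = 14.0% |
| 50% | 0.10 × 0.50 = 5.0% | 0.40 × 0.50 = 20.0% |

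The highest values attainable are 1 − c for acquisition and e for clearance. If every eligible subject cleared, the row could still show only 20% to 50%. For MRSA the effect on clearance is far larger: at an assumed 2% eligible, 0.40 × 0.02 = 0.8%. Missing presurgery results lower acquisition further: with c = 35% and an assumed 10% missing, the factor is 0.65 × 0.90 = 0.585.

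**Between arms, equal at-risk rates.** As a simplification, take one carriage figure per arm for both c and e.

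- Carriage 30% on SA4Ag and 35% on placebo: acquisition RR = 0.70/0.65 = 1.08; clearance RR = 0.30/0.35 = 0.86.
- Carriage 20% and 35%: acquisition RR = 0.80/0.65 = 1.23; clearance RR = 0.20/0.35 = 0.57.
- Equal carriage: the factors cancel and the RR is unchanged. The risk difference still shrinks by 1 − c or by e.

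**Power, equal carriage.** Take 2700 per arm (6000/2 × 0.90, from the planned enrollment and dropout in Protocol Section 9.2), share 35%, two-sided 5%, unstratified comparison of proportions. For acquisition of 10% vs 8%, power is 54.4% with the at-risk denominator and 53.0% with the SAP's. For clearance of 30% vs 35% it is 64.1% and 52.6%. SAP Section 8.1.3.5 records that enrollment ceased at the interim analysis, so 2700 is a planning figure only.

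**The case against.** Four points can fairly be made for the plan.

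First, the conditional wording ("given that the results for the vaccination and presurgery visits were both negative" and "given that all preceding swabs were positive") might mean that the denominator sentence applies only within the eligible group, as a missing-data rule. That reading is possible. However, SAP Section 6.3.3 names the restricted denominator when it wants one, for example readmitted subjects for ICU stay during readmission. At best the text is ambiguous.

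Second, SAP Section 8.2.3.4 plans subgroup analyses of acquisition and clearance by baseline colonization status. Protocol Section 9.3.4.2 defines baseline negative as negative on every swab at Visit 1 and at the Visit 2 admission sample, with none missing. If that definition is used, the subgroup is very nearly the at-risk set for acquisition. This largely stands. It does not help clearance, because one positive swab makes a subject baseline positive, which is broader than all earlier swabs being positive. Also, Section 8.1.3.4 and Table 25 describe the subgroup model only for the proportion colonized, and only for S aureus overall.

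Third, restricting to subjects negative before surgery selects on a result obtained after randomization. The all-swabbed proportion avoids that selection and answers a legitimate, though different, question. This stands and shapes the fix.

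Fourth, Visit 1 carriage is balanced in expectation, and Section 6.3.4 already tabulates colonization by visit and arm, so a presurgery imbalance would be visible. This also stands.

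A reader might go further and infer that the vaccine comparison is biased, or that the efficacy result is affected. The documents support neither. Bias in the RR needs a carriage difference between arms, which the documents do not report, and neither endpoint enters any decision rule.

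**Conclusion.** The mismatch between definition and denominator is real and nothing in the SAP removes it from the main analysis. Read literally, the absolute proportions are understated: by a factor of 0.80 to 0.50 for acquisition and 0.20 to 0.50 for clearance over the assumed 20% to 50% range. Clearance is the weak point, and MRSA clearance most of all. Acquisition is mostly covered by the baseline-negative subgroup.

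The relative comparison is distorted only if presurgery carriage differs between arms; the RRs of 1.08 and 0.86 illustrate an assumed 5-point gap. The at-risk rates, carriage shares, missingness and numbers per arm are all assumptions. The endpoints are exploratory, so the consequence is misread colonization tables, with no effect on the primary conclusion.

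**What to change.** Amend the two denominator sentences in SAP Section 6.3.4:

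- Acquisition: subjects negative at both the vaccination and presurgery visits who have a swab result at the visit concerned.
- Clearance: subjects whose earlier swabs were all positive and who have the two swabs needed to judge clearance at that visit.
- Report the number eligible per arm beside each proportion.
- Keep the all-swabbed proportion as a supporting summary, labelled as the share of all swabbed subjects, because eligibility depends on swabs taken after vaccination.

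No new data are needed. The cost is two sentences and one extra set of table rows. The drawback is that the at-risk comparison is not fully protected by randomization; the eligible counts and the supporting summary let the reader judge how far that matters.

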#### **6.3.4. Colonization with *Staphylococcus aureus***

If 2 or more samples associated with postsurgery are obtained, only the colonization results from the latest visit will be eligible for analysis.

Four colonization endpoints, based on colonization results from scheduled visits, are specified:

1. The number and proportion of subjects in each vaccine group determined to be colonized with *S aureus* on each scheduled visit where swab samples are collected. Colonization at each visit will be compiled separately for each anatomical site, and for any anatomical site. A subject will be considered positive for “any anatomical site” if either site, or both, is positive.
2. Subject carriage status will be characterized across visits as persistent, indeterminate, intermittent, or noncarrier. Characterizations will be performed by anatomical site and any anatomical site. Characterizations will be based on number of visits where colonization results were obtained, limited to Visits 1, 2 (both the day of surgery and the day of discharge), 4 (Day 42), 5 (Day 90), and 6 (Day 180). Rules for determining carriage status are described next and are also illustrated in [Table 7](#).
  - Persistent: positive at 4 of 5, 5 of 5, 5 of 6, or 6 of 6 visits.
  - Indeterminate: exactly 3 or 4 visits, regardless of combination of positive/negative results.
  - Intermittent: positive at 1 or 2 visits if 2 visits are available, positive at 1 to 3 visits if 5 visits are available, positive at 1 to 4 visits if 6 visits are available.
  - Noncarrier: no positive results at any visit, minimum of 5 visits.

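### SAP 6.3.4 codes isolates that are neither CP5 nor CP8 as missing rather than negative for both types, which misclassifies some subjects in the optional capsule-type clearance, carriage and acquisition endpoints

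*SAP*

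**What the plan says.** The rules are all in SAP Section 6.3.4. Below Table 7, the plan says capsule type will be identified for each *S aureus* "isolate as either CP5 or CP8", and adds: "A small subset of isolates will be neither capsule type, so these isolates will be considered missing for capsule type". The next sentence is "Carriage status, acquisition, and clearance will be obtained for each capsule type". The plan then says that analyses of these capsule-type endpoints are possible; it does not commit to them.

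The definitions that this coding feeds are:

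- Clearance: "Clearance is defined as 2 consecutive postbaseline negative swabs, given that all preceding swabs were positive".
- Acquisition: a positive swab after surgery, "given that the results for the vaccination and presurgery visits were both negative".
- Noncarrier: "no positive results at any visit, minimum of 5 visits".
- Indeterminate: "exactly 3 or 4 visits, regardless of combination of positive/negative results".

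Two other sections matter. SAP Section 7 rules out imputation of colonization variables. SAP Section 8.1.3.4 treats Indeterminate as missing in the carriage-status test. Neither document says that an isolate typed as something other than CP5 or CP8 counts as negative for those types.

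**The concern.** Missing should mean that the result is not known. Here it is known: the isolate was typed and is neither CP5 nor CP8. For an endpoint that asks whether a subject carries CP5 at a visit, the answer is no.

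The vaccine contains CP5 and CP8 conjugates (Protocol Section 1.2.3). A capsule-type carriage analysis would therefore be expected to show loss of those two types, including loss by replacement with another type. Visits that show such replacement are the ones this rule sets to missing. What is at stake is the correctness of the capsule-type endpoints if they are analysed. The efficacy conclusions are not at stake.

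**Working it through.** **Inputs.** The six visits are Visit 1, Visit 2 admission, Visit 2 discharge, Day 42, Day 90 and Day 180 (SAP 6.3.4). The carriage rules are those of Table 7. Assumptions: a missing capsule-type result is skipped; a CP8 isolate counts as negative for CP5, and the reverse; postbaseline means after Visit 1; a subject with no countable visit, a case Table 7 does not list, is Missing. The plan gives no figure of its own to reproduce.

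**1. Clearance.** Take subjects with CP5 at Visit 1 and only CP5 or neither-type isolates afterwards, with at least one neither-type isolate. There are 2^5 − 1 = 31 such patterns.

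- As written: every non-CP5 result is missing, so no pattern contains a negative and clearance is scored in 0 of 31.
- Coded negative: clearance needs the first neither-type visit to be followed at once by another. If the first is visit 2 of 6, visit 3 is fixed and three visits are free, giving 8 patterns; if visit 3, 4; if visit 4, 2; if visit 5, 1. The total is 8 + 4 + 2 + 1 = 15 of 31.
- If postbaseline means after Visit 2 admission, the first term goes: 4 + 2 + 1 = 7 of 31, still against 0.

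If culture-negative swabs are also allowed, there are 3^5 − 2^5 = 243 − 32 = 211 patterns with at least one neither-type isolate. Clearance is then scored in 75 as written and in 145 under negative coding. All these are counts of possible patterns, not expected frequencies.

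**2. Carriage status for CP5.** With *k* neither-type visits of six, 6 − *k* visits remain countable as written.

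| *k* | Other visits culture-negative: as written | Coded negative | Other visits CP5: as written | Coded negative |
|---|---|---|---|---|
| 0 | Noncarrier | Noncarrier | Persistent | Persistent |
| 1 | Noncarrier | Noncarrier | Persistent | Persistent |
| 2 | Indeterminate | Noncarrier | Indeterminate | Intermittent |
| 3 | Indeterminate | Noncarrier | Indeterminate | Intermittent |
| 4 | Missing | Noncarrier | Intermittent | Intermittent |
| 5 | Missing | Noncarrier | Missing | Intermittent |
| 6 | Missing | Noncarrier | Missing | Noncarrier |

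An example joins steps 1 and 2. Suppose CP5 is found at Visit 1, admission and discharge, and a neither-type strain at Days 42, 90 and 180. As written, three visits count, so the status is Indeterminate and no clearance is scored. Coded negative, CP5 is positive at 3 of 6 visits (Intermittent) and has been cleared.

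**3. Acquisition.** Both presurgery results must be negative. A subject with a neither-type isolate at Visit 1, at admission or at both, who carries CP5 after surgery, fails that condition as written. Under negative coding the same subject is scored as acquiring CP5.

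**The case against.** The strongest objection is that the plan sets the isolate, not the visit, to missing. Carriage status is based on visits at which a colonization result was obtained, and a swab that grew a neither-type strain did yield a result. On that reading the visit still counts, and the carriage error disappears. The SAP does not say how Table 7 visit counts carry over to capsule type, so the reading is open. It is not the natural one, however: a programmer told that the value is missing for capsule type would set the CP5 and CP8 indicators to missing. That two readings exist is itself a reason to settle the sentence.

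A second objection concerns denominators. For acquisition and clearance, the denominator is subjects with at least one nonmissing swab result, so these subjects may stay in as non-events. This stands, but they are then counted as non-events when they should be events.

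A third is reach. Capsule type appears neither in the colonization methods (SAP 8.1.3.4) nor in Table 25, and the end of Section 6.3.4 suggests that capsule typing may be confined to infections with confirmed *S aureus*. Protocol Section 7.3.4 says only that swab isolates may be evaluated further. This stands in full, and it keeps the point minor.

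Three stronger inferences are tempting but not supported.

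- That replacement of a vaccine type is never scored as clearance. Switches between CP5 and CP8 are outside the rule, and a subject with two later culture-negative swabs can still be scored, for example CP5, CP5, neither, negative, negative, negative.
- That all carriers of other types drop out. One such visit in six leaves five countable visits and a valid status, and two CP5 visits with four neither-type visits give Intermittent under either coding.
- That the results are biased towards no effect. This needs a vaccine-induced shift to other types, which the documents do not show. The coding can also add a clearance: for CP5, neither, CP5, negative, negative, negative, skipping the second visit gives clearance and negative coding does not.

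**Conclusion.** The coding is wrong for type-specific endpoints. If missing results are skipped, it misstates clearance after direct and lasting replacement by a neither-type strain, carriage status when such isolates occur at two or more visits (with the exceptions in the table), and acquisition when one occurs before surgery.

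The number of subjects affected cannot be given. The SAP describes the share of such isolates only as small, and SAP Section 8.1.3.5 records that enrollment ceased in December 2018, so the planned 6000 is not a safe base. The direction of any bias between arms cannot be given either.

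The consequences are confined to optional exploratory capsule-type analyses. No primary or secondary efficacy result, and no colonization result for any *S aureus*, MRSA or MSSA, depends on the rule. It is a low-priority correction, worth making because it is cheap and the rule as stated gives wrong derived values.

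**What to change.** Replace the sentence on neither-type isolates in SAP Section 6.3.4 with:

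*Isolates typed as neither CP5 nor CP8 form a separate category (other capsule type) and count as negative for CP5 and for CP8 in capsule-type carriage status, acquisition and clearance. Only isolates that were not typed, or that have no valid typing result, are missing.*

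If colonization isolates are typed, report the proportion of subjects carrying another capsule type by arm. In the same edit, reconcile the statement that each isolate will be typed with the later sentence that may limit capsule typing to confirmed *S aureus* infections.

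The cost is one sentence and one derivation rule. No typing is needed beyond what the capsule-type endpoints already require, although the documents do not assure that swab isolates will be typed at all.

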**8.2.3.4. Colonization with *Staphylococcus aureus***

All analyses will be performed using the mITT colonization population.

The proportions of subjects with positive swabs will be plotted against time point. The time points' labels on the figures will be "Day of Vaccination," "Day of Surgery," "Day of Discharge," "Day 42," "Day 90," and "Day 180." The values for the time points will be -15, 1, 2, 42, 80, and 180. The legend will identify anatomical site (nasal/oropharyngeal/combined). Plots will be created for "any *S aureus*," MSSA, and MRSA.

Subgroup analyses will be performed on colonization, carriage status, acquisition, and clearance. The subgroups will be age group, sex, baseline colonization status, and primary endpoint (case or noncase). The subgroup analysis of the primary endpoint will be limited to scheduled visits within 90 days, as per definition of the primary endpoint.

A further subgroup will be defined by subjects having any decolonization measures or preadmission antimicrobial agent(s) before surgery (response = yes/no). These analyses will be performed only for "any *S aureus*."

The analysis of matching isolates from microbiologically confirmed cases will be performed separately for nose and throat for each of the efficacy endpoints (BSI and/or deep incisional or organ/space SSI within 90 days, BSI and/or deep incisional or organ/space SSI within 180 days, SSI within 90 days, SSI within 180 days, ISA disease within 90 days, and ISA disease within 180 days), but limited to subjects in the mITT colonization population. If there may be more than 48 cases for the primary endpoint, ie, with BSI and/or deep incisional or organ/space SSI, these extra cases will be included in this analysis.

Colonization analyses and their statistical tests are summarized in Table 25.

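### Discarding swabs after an endpoint infection leaves most primary-endpoint cases Indeterminate or Missing for carriage status, so the planned carriage comparison within cases is sparse and selected, and the discard rule omits clearance

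*SAP*

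**What the plan says.** SAP 6.3.4 classifies each subject's carriage from scheduled swabs, "limited to Visits 1, 2 (both the day of surgery and the day of discharge), 4 (Day 42), 5 (Day 90), and 6 (Day 180"). That gives six time points at most. The text after Table 7 then removes some of them: "Colonization results obtained after a culture-confirmed efficacy endpoint will not be included in deriving characterizations or acquisition". Swabs from a BSI/SSI assessment visit cannot fill the gap either, because the same paragraph adds: "Results from unscheduled visits will not be included in characterizations for persistence, intermittent, etc".

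The classification rules in 6.3.4 and Table 7 agree with each other:

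- Short records of three or four visits are set aside: "Indeterminate: exactly 3 or 4 visits, regardless of combination of positive/negative results"
- A record of only two visits counts as Intermittent when at least one is positive, and as Missing when neither is (Table 7).
- Persistent requires 5 or 6 available visits.
- A subject with no positive swab also needs a long record: "Noncarrier: no positive results at any visit, minimum of 5 visits"

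SAP 8.1.3.4 says that Indeterminate "will be considered a missing value. Vaccine groups will be compared using the CMH test". SAP 8.2.3.4 then plans subgroup analyses of colonization, carriage status, acquisition and clearance: "The subgroups will be age group, sex, baseline colonization status, and primary endpoint (case or noncase"). The case/noncase subgroup uses only scheduled visits within 90 days.

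**The concern.** Primary-endpoint cases have onset on Days 1-90 (SAP 6.1). Each rule is reasonable taken alone, but together they remove most of a case's later swabs. They then treat the short record that remains as uninformative. Most noncases with complete swabs keep five visits. The case level of the planned subgroup would hold few subjects, and those retained would depend on their swab results. A vaccine comparison of carriage status within that level could not be interpreted.

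The second issue is the scope of the discard rule. It covers characterizations and acquisition. Clearance is a separate endpoint in 6.3.4 and is not named. Swabs judged unusable for two endpoints after an infection would still count for the third.

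**Working it through.** **Case count.** Protocol 9.2 expects about 6000 subjects to yield 48 cases, with placebo incidence 1.4%, VE 70% and 10% dropout. Check: 48 / [0.014 × (1 + 0.30)/2] / 0.90 = 48 / 0.0091 / 0.90 = 5861, close to 6000. I use 48 for the planned final analysis and 24 for the interim. SAP 8.1.3.5 records that the trial met its futility criteria at the interim analysis.

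**Countable swabs by onset time.** Visit 4 falls on Days 35-49, Visit 5 on Days 83-97 and Visit 6 on Days 178-192 (Protocol 3). Visit 6 can never precede an onset by Day 90. With complete swabs:

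| Onset | Swabs that count | Visits | Status |
|---|---|---|---|
| Before discharge swab | Visit 1, day of surgery | 2 | Intermittent if either positive; Missing if neither |
| After discharge swab, before Visit 4 | plus discharge | 3 | Indeterminate |
| After Visit 4, before Visit 5 | plus Visit 4 | 4 | Indeterminate |
| After a Visit 5 swab on Days 83-90 | plus Visit 5 | 5 | Classifiable |

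**Onset days in each row.** Inputs: onset Days 2-90 (89 days), discharge on Day 3-7 (assumed), Visits 4 and 5 at the early, nominal or late end of their windows, and a same-day swab either kept or dropped. Example with discharge Day 5, Visit 4 Day 42, Visit 5 Day 90 and same-day swabs kept: 3 days give two visits, 37 give three, 48 give four and 1 gives five. So 37 + 48 = 85 of 89 days lead to Indeterminate. Across all settings, 76 to 88 of the 89 days do, 1 to 6 give two visits, and 0 to 8 give five.

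**Share of cases.** Onset days are not equally likely, and the documents give neither the onset distribution nor length of stay in days. Two sets of assumptions:

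1. Let *a* be the share with onset before the discharge swab (0-20%). Let *q* be the chance that at least one of those two visits is positive (20-50%, borrowing the colonization range in Protocol 1). Let *b* be the share with onset after a Visit 5 swab (0-8%). Usable share = *a* × *q* + *b*; Indeterminate share = 1 − *a* − *b*. The upper end is 0.20 × 0.50 + 0.08 = 0.18, or 8.6 of 48 and 4.3 of 24. The lower end is 0. Indeterminate runs from 1 − 0.20 − 0.08 = 72% to 100%.
2. Early-skewed onset, as a truncated exponential from Day 1. With mean 14 days and discharge on Day 7, the share before discharge is (1 − e^(−6/14)) / (1 − e^(−89/14)) = 0.349, so about 65% are Indeterminate. With mean 30 days and discharge on Day 3, the share before discharge is (1 − e^(−2/30)) / (1 − e^(−89/30)) = 0.068, so up to 93% are Indeterminate. In the first setting with *q* = 0.50, usable cases are (0.349 × 0.50 + 0.001) × 48 = 8.4, within the range already found.

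**Clearance.** SAP 6.3.4 defines clearance as two consecutive negative postbaseline swabs after all earlier swabs were positive. A case positive at Visit 1, surgery and discharge, infected before Visit 4, and negative at Visits 4 and 5 qualifies. An upper bound on the overall distortion, from the plan's own figures: 6000 × 0.90 / 2 = 2700 per arm; placebo cases 2700 × 0.014 = 37.8; vaccine cases 37.8 × 0.30 = 11.3; excess 26.5. If 20-50% of these are colonized and all clear, the excess is 5 to 13 subjects, or 0.2-0.5% of an arm.

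**The case against.** The best defence is that the loss touches very little. SAP 8.1.3.4 describes the colonization subgroup work as a search for vaccine effects that differ between subgroup levels. The only subgroup model it specifies is logistic regression on the proportion colonized, and Table 25 lists no other subgroup row. Per-visit colonization by case status is outside the discard rule. Carriage and infection are also examined elsewhere: efficacy by baseline colonization, efficacy by colonization at surgery (SAP 8.2.1), and strain matching between colonizing and infecting isolates. All of this stands, and it limits the weight of the point. A reader might infer that the subgroup was meant to show whether persistent carriers are the ones who become infected. The documents set no such objective.

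The noncase side is not secure either. If the 90-day limit means actual day, a noncase swabbed for Visit 5 on Days 91-97 has 4 visits and is also Indeterminate. That is a further reason to reconcile the passages.

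On clearance, a reader might infer that clearance among cases reflects treatment of the infection rather than the vaccine. The documents do not establish this; Protocol 6.4.2 says only that antibiotic therapy is recorded. The inconsistent scope of the exclusion is enough to support the point.

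None of this removes the conflict: SAP 8.2.3.4 still names carriage status among the endpoints to be analysed by case and noncase.

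**Conclusion.** The point holds in limited form. With complete swabs, every primary-endpoint case with onset between the discharge and Visit 5 swabs is Indeterminate and analysed as missing. That follows from the rules without any assumption. The size does need assumptions about onset timing, length of stay and swab positivity: roughly 65-100% of cases are Indeterminate, and 0 to 8.6 of 48 (0 to 4.3 of 24) have a usable status.

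A reader might go further and conclude that the case level is empty by construction, or that carriage status always needs five or six visits. Table 7 does not support either reading. Two visits with a positive result is Intermittent, and a late onset after an early Visit 5 swab leaves five visits. Missed swabs can also reduce a case to two visits.

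These routes do not rescue the comparison. Early-onset cases are kept only if swab-positive, and then only as Intermittent. Apart from the few late onsets, no case with complete swabs can be Persistent or Noncarrier. The within-case comparison of vaccine groups is therefore both sparse and selected on swab result.

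The clearance gap is small overall (at most about 0.2-0.5% of an arm under the assumptions above) but matters within the case subgroup. Both issues are confined to exploratory analyses. Primary and secondary efficacy are unaffected.

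**What to change.** Amend the SAP wording; no new data are needed.

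- For the case/noncase subgroup, replace the Table 7 categories with a measure from swabs that precede postoperative infection in every subject: the number of positive visits out of 2 (Visit 1 and Visit 2 admission). State how a missing swab is handled and which model is used. The alternative is to drop carriage status from this subgroup. The discharge swab should not be added, because it follows infection when onset occurs in hospital.
- Extend the post-endpoint exclusion in 6.3.4 to clearance.
- Say whether the 90-day limit in 8.2.3.4 refers to the scheduled visit or the actual day.

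The cost is a coarser carriage measure. Visit 1 precedes vaccination, so any vaccine effect within this subgroup would rest on the admission swab alone. If that is too little to be worth reporting, dropping the carriage-status subgroup is the simpler choice.
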